## **SAMPLE SIZE DETERMNATION AND DATA ANALYSIS**

The sample size calculations are based on responder rates from previous studies of non-invasive neurostimulation in migraine (Lipton et al., 2010; Saper et al., 2011). The numbers used were 15% for sham, based on published trials and 55% for the supraorbital neurostimulation inferred from the pilot study (Gerardy et al., 2009; Lipton et al., 2010; Saper et al., 2011) and 12.1% for sham vs 38.1% for verum in the RCT (Schoenen et al., 2013). To detect a significant difference between the 2 treatments (5% significance level) with an 80% power, the minimum size of each treatment group was estimated at 26 patients, 52 in total who get randomized and initiate the intervention. To account for possible dropouts in the category "randomized, but never started the intervention", we plan to randomize in total 60 patients. To account for patients who do not meet the eligibility criteria at screening, we anticipate we will need to consent about 75 patients.

Statistical analysis will be carried out on an intention-to-treat basis, as well as per protocol for comparison. For Aim 1, the primary comparison will be the between-group comparison at the end of month 2 of the tDCS/sham intervention for the primary and secondary outcomes measures (listed in detail on pgs 7,8). Secondary exploratory comparisons will include between-group comparisons at the month 1 (Day-30) of the 2-month intervention, and within groups comparisons across the study time-points (the baseline, month 1, month 2), as well as comparison of efficacy in patients with chronic and episodic migraines and comparison of efficacy in patient taking abortive migraine medications on 10 or more days with those taking them on 9 or fewer days.

For Aim 2, (Satisfaction with the device and procedure), the primary analysis will include the between-group comparison of at the end of month 2 of the tDCS/sham intervention, evaluating the percentage of patients stating at the end of the trial that they are very satisfied, moderately satisfied, or not satisfied with the device use and procedure, determined from the 8-item tDCS User Survey at the end of the intervention. (We anticipate significant group differences in Survey items pertaining to being more confident in symptom management at home, but no significant group differences in items pertaining to satisfaction with tDCS training and ease of use of the device). In addition, the

process data - number of delivered applications and the protocol fidelity in each study group will be analyzed, in order to support evidence on feasibility of the procedure.

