## **OUTCOME MEASURES AND ENDPOINTS**

Outcome assessment time-points will be at the end of the 30-day baseline ( $\pm 2$  days), at the end of month 1 (day  $30 \pm 2$  days, the secondary end-point) and month 2 (day  $60 \pm 2$  days, the primary end-point) of the tDCS/sham intervention.

The primary comparison will be the between-group comparison at the end of month 2 of the tDCS/sham intervention.

**The primary outcome measure** will be *Change in mean number of migraine days per month.*

A note: A migraine day is defined as any calendar day on which the patient had onset, continuation, or recurrence of a migraine as recorded in the diary. A migraine is defined as a migraine (with or without aura) lasting at least 30 minutes. Any calendar day on which acute migraine medication is used is counted as a migraine day.

**Secondary outcome measures** will be:

1. *Percentage of responders*, determined as a number of patients having at least 50% reduction of monthly migraine days between the one-month baseline and post-intervention, in each of the two study groups;
2. *Change in monthly migraine attack frequency*,
3. *Change in monthly acute antimigraine drug use*,

all determined from the patients' diaries;

4. *Change in mean headache severity per migraine day* determined from Pain NRS ratings on migraine days;
5. *Change in quality of life* determined from ratings on the migraine-specific MSQ questionnaire;
6. *Change in depressive symptoms* determined from the Hamilton Depression Scale (HamD);
7. *Tolerability* determined from occurrence of side effects and adverse events related, probably related or possibly related to tDCS, through the study;
8. *Satisfaction* - percentage of patients stating at the end of the trial that they are very satisfied, moderately satisfied, or not satisfied with the treatment, determined from the 8-item tDCS User Survey at the end of the intervention;

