## Analysis Plan (Update 1.29.20)

Participants will be randomized within randomly selected blocks of sizes 2, 4, and 6. The randomization list will be generated by an investigator not otherwise associated with the administration of treatment or collection of data.

All patient characteristics and outcomes will be evaluated for distribution. For all bivariate tests, the appropriate parametric or non-parametric test will be selected based on distribution. Patient characteristics will be described and bivariate tests will evaluate any differences across treatment group (active tDCS vs. sham tDCS). Primary and secondary outcomes at baseline will be described and bivariate tests will evaluate any differences across group. Bivariate tests will evaluate differences in attrition, patient satisfaction, adverse events (including all adverse events, serious adverse events, and adverse events attributed to the treatment), and quality of blinding across group.

All outcomes will be described using data visualization. Differences in outcome between the active tDCS and sham tDCS groups will be evaluated in both intent-to-treat and completer analysis using non-parametric statistics as appropriate (see Table below). Intent-to-treat analysis will impute missing values using all available data. Differences in outcome between people with chronic (15 or more headache days/month) vs. episodic migraine, with and without medication overuse (e.g., using a MSM on 10 or more days per month during the baseline period), and with high and low levels of patient compliance will also be evaluated using the appropriate non-parametric statistic.

Alpha will be set at 0.05, two-tailed, for all analyses. SPSS v. 25.0 and R will be used for all analyses.

Primary Outcome	Description	Tentative Analysis Type
Change in migraine day/30 day	Median change in the number of migraine days per 30 day period, from M0 to M2.	Mann-Whitney U
Secondary Outcomes		
Responders	% of participants who report a 50% reduction in migraine days, from M0 to M2.	Fisher's Exact Test
Change in headache attack/30 days	Median change in number of attacks per 30 day period, from M0 to M2.	Mann-Whitney U
Change in acute medication use	Median change in number of days on which an acute medication was used from M0 to M2.	Mann-Whitney U
Change in headache attack intensity	Median change in NRS from headache days in a 30 day period from M0 to M2.	Mann-Whitney U

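### The sample size of 26 per arm gives 80% power for only one of the two responder-rate pairs listed as its inputs; at 12.1% vs 38.1%, Fisher's test has 47% power at 26 per arm and 55% at 30

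*Protocol*

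**What the plan says.** The protocol's section on sample size and data analysis opens with the basis of the calculation: "The sample size calculations are based on responder rates from previous studies of non-invasive neurostimulation in migraine". Two pairs of rates follow in one sentence. The first is "The numbers used were 15% for sham, based on published trials and 55% for the supraorbital neurostimulation inferred from the pilot study". The second, joined to it, is "12.1% for sham vs 38.1% for verum in the RCT".

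The next sentence gives a single result for 80% power at a 5% significance level: "the minimum size of each treatment group was estimated at 26 patients, 52 in total who get randomized and initiate the intervention". To allow for patients who are randomized but never start, the section adds "we plan to randomize in total 60 patients". It does not say which pair, formula or sidedness produced 26.

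Under Outcome Measures and Endpoints, the primary outcome is "Change in mean number of migraine days per month". The responder percentage is the first secondary outcome, "determined as a number of patients having at least 50% reduction of monthly migraine days between the one-month baseline and post-intervention".

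The SAP sets alpha at 0.05, two-tailed, for all analyses. Its table gives Fisher's exact test for the percentage "of participants who report a 50% reduction in migraine days, from M0 to M2" and a Mann-Whitney U test for the primary outcome. The column that names the tests is headed as tentative.

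**The concern.** The two pairs imply very different trials. The first is a 40-point difference, with the active rate inferred from a pilot study. The second is a 26-point difference from a randomized trial. One sample size cannot give 80% power at both, yet a reader would take the stated power to cover the inputs listed just before it.

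If the randomized-trial rates are nearer the truth, the responder comparison has roughly an even chance of missing the effect. A non-significant result could then be reported as an adequately powered negative, although it would not exclude an effect that the protocol itself cites.

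This is also the plan's only sample size justification, and it is for a secondary outcome. For the primary outcome the reader has no stated basis for judging what a null result would exclude.

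**Working it through.** **Inputs.** Rates 15% vs 55% and 12.1% vs 38.1%, 5% level, 80% power, 26 and 30 per arm (60 randomized, 1:1): protocol, sample size section. Two-tailed 0.05 and Fisher's exact test: SAP.

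**Formula.** With d = p2 − p1 and p̄ = (p1 + p2)/2, the pooled-variance size per arm is

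n = [z_α √(2p̄(1 − p̄)) + z_β √(p1(1 − p1) + p2(1 − p2))]² / d²,

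and the continuity-corrected size is n_c = (n/4)[1 + √(1 + 4/(n d))]². Two-sided z_α = 1.960, one-sided z_α = 1.645, z_β = 0.842.

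**Step 1: reproduce the plan's 26 (15% vs 55%, two-sided).** p̄ = 0.35, d = 0.40.
- n = (1.3221 + 0.5154)² / 0.16 = 21.1
- n_c = (21.1/4)(1 + 1.2140)² = 25.86, which rounds up to 26. This is the stated figure.

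**Step 2: the same formula for 12.1% vs 38.1%.** p̄ = 0.251, d = 0.26.
- n = (1.2018 + 0.4923)² / 0.0676 = 42.5, so 43 per arm
- n_c = (42.46/4)(1 + 1.1672)² = 49.9, so 50 per arm

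**Step 3: could another convention give 26 for the second pair?** The protocol does not state sidedness, so one-sided versions were tried too.

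| Variant, 12.1% vs 38.1% | Two-sided | One-sided |
|---|---|---|
| Unpooled | 40 | 32 |
| Arcsine | 41 | 33 |
| Pooled | 43 | 34 |
| Continuity-corrected | 50 | 41 |

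None gives 26.

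**Step 4: power of the test in the SAP.** For every pair of responder counts, take the two-sided Fisher p-value and add up the binomial probabilities of the tables with p ≤ 0.05. The uncorrected chi-square test is done the same way for comparison.

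| Rates | Test | 26 per arm | 30 per arm |
|---|---|---|---|
| 15% vs 55% | Fisher | 82.4% | 87.6% |
| 12.1% vs 38.1% | Fisher | 46.7% | 55.3% |
| 12.1% vs 38.1% | Chi-square, uncorrected | 61.8% | 66.1% |

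For 12.1% vs 38.1%, Fisher power is 79.9% at 48 per arm and 81.0% at 49. With sham held at 12.1%, 80% Fisher power needs an active rate of about 50.2% at 26 per arm or 46.8% at 30 per arm, against the listed 38.1%.

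**Step 5: the primary outcome.** The documents give no standard deviation for change in migraine days, so only a standardized figure is possible. Under an assumed normal shift, a two-sample t-test has 80% power at 0.792 SD (26 per arm) or 0.736 SD (30 per arm). Dividing by √(3/π) = 0.977, the large-sample adjustment for Mann-Whitney, gives 0.81 SD and 0.75 SD. A simulation with 20,000 samples gave power of 80.0% and 79.2% at those shifts.

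**The case against.** The best reply is that nothing has been miscalculated. The 26 follows exactly from the first pair listed, and the protocol never says in terms that 80% holds at both pairs; the randomized-trial rates may be there as background. It is right that 26 is a correct result for 15% vs 55%. But the sentence presents both pairs as the numbers used, and a single power figure follows. If the second pair was not used, the paragraph needs correcting for that reason.

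A second reply is that Fisher's test is conservative and the SAP marks its choice of tests as tentative. That moves the figures: under the uncorrected chi-square test the chance of missing the effect is about 38% at 26 per arm and 34% at 30, rather than 53% and 45%. It does not bring power to 80%.

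A third is that 60 patients are randomized, not 52. The extra eight are an allowance for patients who never start, and with all 60 analysed Fisher power is still 55.3%.

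Finally, the responder rate is secondary, so these powers say nothing direct about the main comparison. That stands. The primary comparison's power is unjustified in the documents, but it has not been shown to be low. The SD figures in Step 5 are illustrative, since migraine days are a bounded count and the normal shift is an assumption.

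**Conclusion.** The point holds and should be fixed. The stated 80% power is correct for 15% vs 55% (82.4% by Fisher at 26 per arm) and wrong for 12.1% vs 38.1%, where it is 46.7% at 26 per arm and 55.3% at 30. Reaching 80% for the second pair would take 49 per arm with Fisher's test.

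The 30-per-arm figures assume that all 60 randomized patients are analysed in equal arms. The shortfall does not depend on the choice of test, on sidedness or on continuity correction; only its size does. The fault is a power statement that does not name its input and does not hold for one of the two inputs listed. It does not invalidate the trial.

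**What to change.** Keep 60 patients and reword the sample size paragraph.

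1. The sponsor confirms which pair and formula gave 26 per arm (by calculation 15% vs 55%, two-sided 5%, continuity-corrected) and states that the 80% applies to the secondary responder outcome.
2. Add a sentence such as: *At 12.1% vs 38.1%, a two-tailed Fisher's exact test has about 47% power at 26 per arm and 55% at 30 per arm, so a non-significant responder result would not exclude an effect of that size.* If the test may still change, give the chi-square figures (62% and 66%) beside these.
3. Alongside, state the detectable difference for the primary Mann-Whitney comparison: about 0.81 SD at 26 per arm and 0.75 SD at 30 per arm for 80% power, labelled as resting on a normal shift. The sponsor supplies an SD so that this can be expressed in days. A clause may add that patients who never start remain in the intention-to-treat analysis, so power also depends on how their values are imputed.

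The cost is one revised paragraph and one SD that the documents do not give. The number of patients, the tests and the conduct of the trial do not change. The stated power becomes less favourable.

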### *Outcome Assessment*

Outcome assessment will utilize the following tools:

- Patients's Daily Diaries will be used to take notes of days on which a migraine attack occurs, duration of the attack, severity of migraine pain during the migraine attack, acute antimigraine drug use, and occurrence of any other (non-migraine) headache. Time needed to fill-in the diary is about 1-3 minutes per day (filled-in only on days when headache or migraine medication intake occur).
- Pain Numerical Rating Scale (Pain NRS) is an eleven point [0-10] scale for rating of pain intensity, with the anchor points 0=no pain and 10=worst pain imaginable. Administration time is about 1 minute, rated only on migraine days.

- Migraine-Specific Quality of Life Questionnaire (MSQ) is a validated 25-item questionnaire evaluating impact of migraine on physical, emotional and social component of patients' life. Recall period is four weeks. Administered at the baseline, at the end of month 1 and month 2 of tDCS/sham application. Administration time is about 5 minutes (Rendas-Baum et al., 2013).
- Hamilton Depression Scale (HamD) is a validated 17-item instrument for assessment of depressive symptoms. Administered at the baseline, at the end of month 1 and month 2 of tDCS/sham application. Administration time is about 20 minutes (Hamilton, 1960; Williams, 1988).
- tDCS User Survey is an 8-item questionnaire on user's satisfaction with the use of tDCS. Administered at the end of tDCS use. Administration time is about 5 minutes.
- Occurrence of side effects and adverse events through the study. Tolerability will be determined from occurrence of side effects and adverse events related, probably related or possibly related to tDCS, through the study.

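### The exploratory medication-use comparison sets high and low users side by side on unadjusted change, although the split itself fixes different baselines; subgroup efficacy should be defined as the active-sham contrast

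*Protocol*

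**What the plan says.** The protocol's analysis section (Sample Size Determination and Data Analysis) lists a "comparison of efficacy in patient taking abortive migraine medications on 10 or more days with those taking them on 9 or fewer days". It gives no period over which those days are counted. The sentence opens with "Secondary exploratory comparisons will include between-group comparisons at the month 1 (Day-30) of the 2-month intervention", so the comparison is exploratory.

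The protocol's outcome section (Outcome Measures and Endpoints) defines the primary count so that "Any calendar day on which acute migraine medication is used is counted as a migraine day".

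The SAP (Analysis Plan, update 1.29.20) places the split before treatment: "with and without medication overuse (e.g., using a MSM on 10 or more days per month during the baseline period". It says that differences in outcome between such people "will also be evaluated using the appropriate non-parametric statistic". The primary outcome in its table is "Median change in the number of migraine days per 30 day period, from M0 to M2", tested by Mann-Whitney U.

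Neither document says whether subgroup efficacy means change pooled over arms, change in the active arm, or active versus sham within each subgroup. Neither plans an arm-by-subgroup term or adjustment for baseline migraine days.

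**The concern.** The variable that forms the subgroups is part of the outcome on which they are compared. A patient with 10 or more baseline medication days must have at least 10 baseline migraine days; a patient in the other group needs only the 4 required for entry. The subgroups therefore differ in baseline by construction, and unadjusted change depends on baseline in two ways.

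- **Regression to the mean.** Patients selected for a high month tend to record fewer days later, with or without treatment.
- **Scale.** The same proportional effect removes more days from a higher starting count.

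A reader could take either one as evidence that tDCS works better in heavy users of acute medication. At stake is the interpretation of one exploratory result, which could be carried into a publication or into the design of a later trial.

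**Working it through.** The plan gives no figure for this comparison. The section's only calculated figure, 26 per group, concerns responder rates and has no bearing here. (It reproduces: 15% vs 55%, two-sided 5%, 80% power gives 22 per arm uncorrected and 26 with continuity correction.)

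**1. Baseline floor, from the documents.** Medication days are a subset of counted migraine days, so counted days ≥ medication days. Upper group: at least 10. Lower group: at least 4, the entry criterion. This takes the SAP's unexpanded abbreviation MSM to mean an acute migraine drug.

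**2. Scale effect at those floors.** Assume a 30% reduction relative to sham in everyone. At 10 days it is worth 0.30 × 10 = 3.0 days; at 4 days, 0.30 × 4 = 1.2 days. The ratio is 0.70 in both.

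**3. Simulation.** The documents give no distribution of migraine or medication days, so these inputs are assumptions: mean 8 or 11 true migraine days per 30; between-patient beta concentration 6; month-to-month beta concentration 30 or 100; medication on about 70% of migraine days and on 0% or 5% of other days. Entry required 4 or more counted days, and the split was at 10 or more baseline medication days. Ranges are across settings, with about 1,000 trials of 60 patients in each. Baseline means were about 16 to 17 days (upper) and 8 to 9.5 (lower).

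| Quantity | Upper group | Lower group |
|---|---|---|
| Mean change, no treatment effect | −1.2 to −2.4 days | 0.0 to +0.8 days |
| Active minus sham, no treatment effect | about 0 | about 0 |
| Active minus sham, 30% effect in everyone | −3.8 to −4.7 days | −2.1 to −3.0 days |
| Sham patients meeting the 50% responder definition | 4% to 14% | 8% to 21% |

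With no treatment effect, the gap in change between subgroups was 1.6 to 2.4 days. Tests giving p<0.05, against a nominal 5%:

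- direct subgroup comparison, arms pooled: 26% to 43%;
- direct subgroup comparison, active arm only: 15% to 22%;
- arm-by-subgroup interaction: about 4% to 6%.

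With the common 30% effect, the interaction test on absolute change rejected in 9% to 14%. A separate simulation under other assumed distributions gave a null gap of about 2.2 to 2.7 days and pooled rejection in 33% to 65% of trials. With a common reduction of 40% active and 15% sham, it gave an active-sham difference of about 3.8 vs 2.1 days at an equal ratio of 0.71 (0.60/0.85 = 0.71).

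**4. Share due to the medication-day rule.** If medication is taken only on migraine days, the rule adds no days and changes nothing. With medication on 5% of other days, dropping the rule moves the null gap from 1.7–2.4 to 1.5–2.2 days, and pooled rejection from 29%–43% to 25%–35%. Most of the artefact remains.

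**5. Dilution by drug days without migraine.** The diary is "filled-in only on days when headache or migraine medication intake occur", so it allows for such days. For h drug days placed at random and m true migraine days, counted days = m + (30 − m)h/30, and the counted active-sham difference is the true one × (1 − h/30). Hypothetical patient: 12 true days at baseline, 10.2 on sham (15% reduction), 7.2 on active (40% reduction); true difference 3.0 days, 3.0/10.2 = 29%.

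| h | Counted sham | Counted active | Difference | Relative to sham |
|---|---|---|---|---|
| 4 | 12.84 | 10.24 | 2.6 | 20% |
| 8 | 15.48 | 13.28 | 2.2 | 14% |
| 12 | 18.12 | 16.32 | 1.8 | 10% |

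The documents give no value for h, so the real size cannot be estimated.

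**The case against.** The strongest reply is that the SAP fixes the split in the baseline period. Randomization then protects active versus sham within each subgroup; under no effect that contrast is about zero and an interaction test keeps its level. This stands. It does not close the gap, because the SAP does not say that this contrast is what it will estimate, and its wording reads as a direct comparison of the two kinds of patient. The protocol sentence also leaves the counting period open.

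A second reply is that a larger absolute benefit in frequent sufferers is a real benefit, and that the plan also has the responder percentage, attack frequency and MSQ. This stands in part: the choice of scale is a judgement, which is why both should be shown. The responder percentage is relative but does not settle the matter, since on sham it favours the lower group while absolute change favours the upper.

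A reader might go further than the documents allow, in four ways.

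- That the definitions alone create a difference in efficacy. They fix only the baseline floor; the rest needs month-to-month variation or a proportional effect read in absolute days. Any split correlated with baseline frequency, such as chronic versus episodic, shares the problem.
- That masking by drug days falls specifically on heavy users. The dilution formula applies to any patient with such days, and a further check found attenuation at least as large in the lower group.
- That the medication secondary outcome, "Median change in number of days on which an acute medication was used from M0 to M2", is offered as independent confirmation of the primary. It shares days with the primary, but no passage uses it that way.
- That the medication-use question cannot be answered at all. With a defined contrast it can be, though imprecisely.

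**Conclusion.** The concern holds for the subgroup comparison as the SAP words it. Under the assumptions in the working, a direct comparison of unadjusted change shows a gap of 1.6 to 2.4 days with no treatment effect and is significant far more often than 5% (26% to 43% with arms pooled). With an equal proportional effect it shows a larger absolute benefit in the upper group. The direction was the same in every setting tried; the sizes depend on assumed distributions.

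Regression to the mean and the absolute scale account for most of this. The medication-day rule adds a smaller part, plus a possible dilution of unknown size. The active-sham contrast within baseline-defined subgroups is not biased under the null, the primary comparison is unaffected, and the analysis is exploratory. The change should be made, but nothing central to the trial depends on it.

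**What to change.** 1. State in both documents that the split uses medication days in the 30-day baseline, and fix the threshold in the SAP, where it now appears only as an example.
2. Define subgroup efficacy as the active-sham contrast within each subgroup, with an arm-by-subgroup term and adjustment for baseline migraine days. One option is a log-link count model of month-2 days on log baseline days, arm, subgroup and their interaction; log baseline is always defined because entry requires at least 4 days.
3. Report the contrast in days and as a ratio.
4. As a sensitivity analysis by arm, repeat it counting only days with a diary-recorded migraine of at least 30 minutes. Leave the primary definition unchanged.

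The cost is a few sentences and a few lines of code. The diary already records attacks and drug use, so no new data are needed. There are two limits. The attack-only count can miss migraines stopped early by medication, so both counts should be shown. With 60 patients the interaction estimate will be imprecise, so the comparison should stay labelled exploratory.
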